## 7.4 Premature attempt abort of a participant

- The participant withdraws his consent
- Death of the participant
- The participant does not follow the study protocol (trains balance outside the intervention)
- The participant has one of the exclusion

If possible, the participant still receives the final medical examination and the reassessments are carried out.

If possible, the participant will be replaced. This means that the next signed declaration of consent takes this place.

Regular visits are always Monday, Wednesday and Friday. If an appointment is missed, the doctor's contact can be made up at any time. If I or the patient sees a requirement for an additional doctor contact, it will be arranged promptly (preferably on the same day).  
STudieninterventionen

## 7.5 General

### Standard therapy

According to the payer, the therapy is individually composed of the following therapies:

Individual Therapies: Speech Therapy (45min), Physiotherapy (30-45), Occupational Therapy (30-45), Neuropsychology (30-180), Physical Therapy (30-60)

Group therapies: Seating group (30), MTT (60), endurance group (45), self-training (30), water aerobics (30), fine motor skills (45), memory group (45), public transport group (135), cooking group (150), arm-hand Group (45), Household Group (45)

Of these, 3-4 therapies are selected Monday-Friday.

### 7.5.1 Experimental intervention

#### Individual balance training (IB)

*Standard course of balance exercises*

1. Stand with a narrow track

- a. Head rotation (30 sec)
- b. Closed eyes (3x10 sec)
- c. Turn head with closed eyes (3x10 sec)

2nd Stand narrow track set half a foot, "load both feet evenly"

- a. Head rotation (30 sec)
- b. Closed eyes (3x10 sec)
- c. Turn head with closed eyes (3x10 sec)
- d. Change of feet: a-c

3rd step, "at least the toes are behind the heel and strain both feet evenly", Spurbreit depending on the level of the patient, very good patients go into tandem

- a. Head rotation (30 sec)

- b. Closed eyes
- c. Turn head with closed eyes (10 sec)
- d. Change of feet: a-c
- 4. Toe stance, "big toe ball stays on the ground and can not take off"
  - a. Head rotation (30 sec)
  - b. Closed eyes (10 sec)
  - c. Turn head with closed eyes (10 sec)
- 5. Stretching calves in step position with hold (2x per side, each 30 sec. Per leg)
- 6. Labile underlay (AirexPad, air cushion)
  - Repeat exercises 1-5
- 7. Patients receive a disinfectant wipe with instructions to wipe the ingot and then the AirexPad.
  - Exercises keeping balance after bending over the pillow

## **7.5.2 Controle intervention**

### **Group balance training (GB)**

The exercise sequence is the same as IB training.

There will be between 3-6 patients. These may have different diagnoses and will not all have a stroke as a basic diagnosis.

## **7.6 Administration of the experimental intervention and the control intervention**

### **7.6.1 Experimental intervention**

#### **Individual balance training**

After the assessments, the intervention starts the next day. Twice a week the participants receive individual balance training with an effective training time of 25 minutes. Between the two days should be at least 1 day break. In total there will be six units. There must be no balance training in the other therapies. Completed with the reassessments, one day after the last IB. To exclude a training effect before the reassessment.

### **7.6.2 Control intervention**

#### **Group balance training**

After the assessments the balance group starts the next day. The exercise sequence corresponds to the single-balance training.

For the study participants, the group will be held twice a week with 25 minutes each of effective training time. There are six units in total. It concludes with the reassessments, one day after the last GB, to exclude a training effect before the Reassessment.

In the individual therapies no balance training may take place.

### **7.6.3 Modificationen of the intervention**

All patients are made aware that their safety is paramount and they should open their eyes if they feel they are losing their balance. They are encouraged to react with a protective step, but may also be able to hold on to the bar.

Therapy is discontinued if the patient wishes he has a fever or has other contraindications to active therapy.

## **7.7 Compliance**

Noncompliant is the patient when performing additional balance exercises during leisure time. This is actively being asked by me and the treating therapist. If this is the case he must be excluded from the study because it might affect the results.

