### **3.2 Experimental intervention und Indication**

The intervention is the balance training. It is carried out by me, or by a trained employee, in the case of my absence. There is a schedule for this, which I attach with. It is standing balance training in a safe setting. So nearby a bar. It is worked with different sized support surfaces. In each position you work with closed eyes and also with head rotation. Patients should be encouraged to take a protective step if they feel they are unbalanced. This balance program is standard in our rehabilitation clinic.

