## **6.5 Mask, Blinding**

There is no blinding. Compliance with the blinding is hardly feasible in this setting. The patients recognize which group they are in and the group room is freely accessible and accessible by my colleagues.

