## 8 TEST METHODS

### 8.1 Schedule of study, Table of study measures

one day before arrival	

• Screening of the remittance findings

Day of arrival	

• Admission by the doctors, nursing and physiotherapy --> Screening Inclusion / Exclusion

2nd Day	

• Discussion and presentation of the consent form

• Information to the therapist that the patient may be eligible

• in physiotherapy only BBS and 10 m walk test if patient has already signed

from the 2nd day	

• Signing of consent (SC)

Day of SC	

• Envelopes draw IB or GB for the allocation

• Report to the scheduling about allocation and notification of the patient

SC +1d	

• Assessment Primary target: Gait speed through 10 m walk test

• Assessment secondary target: Fall risk due to BBS, walkability due to FAC

SC +2d	

• IB or GB so that it can be found twice a week (see point 8.2)

6. IB/GB	

• next day reassessments

• 10 m walk test, BBS, FAC

Visitation	

• see point visitation plan

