### **10.3 plannend analysis**

For the pilot study mainly the BIAS (systemic errors) should be analyzed.

These could turn out to be selective or during the test procedure. But of course also in the amount of data collected.

The collected records are also discussed.

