### **10.3.2 Primary analysis**

The analysis will be carried out by the investigator after completion of the entire intervention.

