## **10.4 Dealing with missing data and drop-outs**

If the data can not be completed, the patient is excluded so as to avoid falsification of the results. The existing data and also the drop-outs will be archived anyway.

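### Patients found self-training are excluded after unblinded allocation, with no planned summary that keeps them in their arm and no count of exclusions by arm

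*Combined protocol and SAP*

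**What the plan says.** Two rules remove patients after randomisation. Section 7.7 (Compliance) treats balance exercise in leisure time as non-compliance and adds: "If this is the case he must be excluded from the study because it might affect the results". Section 10.4 deals with missing data: "If the data can not be completed, the patient is excluded so as to avoid falsification of the results". It then says only that existing data and drop-outs will be archived.

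Both rules act with the allocation known. In the section 8.1 schedule, "Envelopes draw IB or GB for the allocation" falls on the day consent is signed, before the first training session. Section 6.5 states "There is no blinding", and section 6.1 has the therapists informed of the allocation. On how self-training is found, section 7.7 says "This is actively being asked by me and the treating therapist". The investigator also gives the training (section 3.2: "It is carried out by me, or by a trained employee, in the case of my absence") and does the analysis (section 10.3.2: "The analysis will be carried out by the investigator after completion of the entire intervention").

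Section 7.4 lists training balance outside the intervention as a reason for stopping early, asks for the reassessments where possible, and lets the next consenting patient fill the place. Section 7.8 times the reassessment after early stopping but names only the Berg Balance Scale and the 10 m walk test, not the FAC.

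Section 10.3 makes bias the main subject of the analysis; of possible biases it says "These could turn out to be selective or during the test procedure", and it also mentions the amount of data. Section 12.1.2 keeps randomisation and reasons for early withdrawal in the source data.

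**The concern.** A randomised comparison is protected as long as patients are compared in the arms they drew. Section 7.7 breaks that protection for a reason that concerns the data. Whether self-training is asked about, admitted and acted on may differ between arms when the people asking know the arm, and patients who exercise on their own may progress differently from those who do not. Removing them can then shift the between-arm difference in either direction.

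Two products of the pilot are exposed. Section 4.2 asks whether the effect differs between individual and group training, and section 10 takes the follow-up sample size from the data collected. Exclusions and drop-outs by arm are also a feasibility result in themselves. Because section 7.4 replaces patients who leave, a final 10 and 10 could hide them.

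**Working it through.** **The plan's own figure.** 10 + 10 = 20 patients (section 10.2). The number was set by the time available. No SD, alpha, power or drop-out rate is given, so there is no calculation to reproduce.

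**Is an excluded self-trainer kept anywhere in the analysis?** Sections 10 to 10.4 name means, standard deviations, frequencies and an odds ratio, but no analysis population. The reason given in section 7.7 points to removal from the analysis. For other early stoppers, section 10.4 can be read in two ways: a patient who stopped but was reassessed counts as complete, or drop-outs are archived and not analysed. On the first reading the loss is mainly the self-trainers; on the second it is larger.

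**Is a count by arm promised?** The nearest provisions are the unspecified frequencies (section 10), the general bias review (10.3), the screening and enrolment logs (12.1.1) and the withdrawal reasons (12.1.2). The data for such a count would exist, but none of these commits to reporting it.

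**Possible size.** Every input except the 10 per arm is an assumption. The 0.18 m/s is the success benchmark for improvement in section 5.1, borrowed as a scale.

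1. Shift in one arm's mean when k of 10 are removed = (k/10) × gap, where the gap is the difference in mean gain between removed and retained patients. With a gap of 0.18 m/s, k = 1, 2, 3 gives 0.018, 0.036, 0.054 m/s. With k = 2, gaps of 0.09 and 0.27 give 0.018 and 0.054 m/s.

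2. Standard error of the difference, 10 per arm = SD × √(2/10).

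| Assumed SD of change (m/s) | Standard error (m/s) | 0.036 as a share of it |
|---|---|---|
| 0.15 | 0.067 | 54% |
| 0.25 | 0.112 | 32% |
| 0.35 | 0.157 | 23% |

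3. Follow-up size if the observed difference is used (two-sample t-test, two-sided 5%, 80% power, true difference assumed 0.10 m/s, SD held fixed). The shifted differences are 0.10 + 0.036 = 0.136 and 0.10 − 0.036 = 0.064 m/s.

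| SD (m/s) | n per arm at 0.10 | at 0.136 | at 0.064 |
|---|---|---|---|
| 0.15 | 37 | 21 | 88 |
| 0.25 | 100 | 55 | 241 |
| 0.35 | 194 | 105 | 471 |

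Chance alone does more. At SD 0.25, one standard error upward gives 0.10 + 0.112 = 0.212 m/s and 23 per arm; one downward gives −0.012 m/s, a reversed sign.

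4. Follow-up size if a fixed target of 0.18 m/s is used. The mean shift then has no effect and only the SD matters. At SD 0.25 the requirement is 32 per arm. In a simulation of 400,000 normal arms of 10 with the two lowest responders removed, the pooled SD with the intact arm falls to 0.915 of its full value, and 32 becomes 27.

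5. In the same simulation the arm mean shifts by 0.318 SD on average (5th to 95th percentile 0.184 to 0.474 SD). At SD 0.25 the average is 0.318 × 0.25 = 0.080 m/s. This is an illustration of strong selection, not a bound.

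**The case against.** The strongest reply is that little hangs on this. The pilot is descriptive, its size was set by time, and section 10.1 admits that the numbers allow only a guess. No confirmatory test depends on the exclusions. The ban on free-time training (section 7.9) and the questioning rule (7.7) apply to both arms alike, and nothing shows how often self-training occurs or which way it acts. The section 5.1 benchmark was not meant as a gap between self-trainers and others. The scenario with the lowest responders selects on outcome, whereas section 7.7 selects on behaviour. It also ignores replacement: filling both places with random patients gives a shift of about 0.25 SD, a pooled SD ratio of 0.93 and 28 per arm. Finally, section 10 is silent on the analysis population, so the excluded patients' values might still be used.

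Much of this stands and limits the severity. The figures show scale only, and differential detection is a possibility, not a finding. Two things remain. An equal rule applied by people who know the arm does not guarantee equal application. And silence about the analysis population, next to a rule that excludes in order to protect the results, more naturally means removal than retention. A pilot whose declared purpose is to find bias should at least count who was removed from each arm.

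**Conclusion.** The point holds and should be fixed; it does not invalidate the pilot. The plan requires post-randomisation exclusion decided with allocation known, defines no summary that keeps those patients in the arm drawn, and commits to no report of exclusions by arm. That rests on the text alone.

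Its size is unknown. On the assumptions above, an imbalance of two patients is worth about a quarter to a half of one standard error of the difference, so it is smaller than chance error. Unlike chance error, it would not average out in a larger trial run under the same rule. Its effect on the follow-up sample size depends on whether that calculation uses the observed difference or a fixed target, which the plan does not say.

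A secondary point is that section 7.4 does not say whether a replacement takes the vacated arm or the next numbered envelope. Section 7.3, which allocates by order of consent, favours the envelope.

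**What to change.** These changes concern analysis and reporting only; they leave open whether a self-trainer continues the training.

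- **Sections 7.7 and 10.4:** summarise all randomised patients with an available reassessment in the arm drawn, including self-trainers, with self-training recorded as a protocol deviation. Judge completeness for each outcome separately, so that a missing FAC does not remove a walking speed. Flag reassessments made before the sixth session, give the number of sessions completed, and show the summary with and without them. Show per-protocol results as secondary.
- **Section 10.3:** as part of the planned bias analysis, report the numbers randomised, excluded and missing by arm, with reasons. Patients without any reassessment stay in these counts.
- **Sections 7.3 and 7.4:** reconcile the two by stating that any additional patient draws the next numbered envelope and that the patient who left stays in the drop-out count. The investigator's access to the randomisation list (7.3) is a separate matter that this does not cure.

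The cost is wording and a small table. No new measurement is needed, because the reassessments, intervention details and withdrawal reasons are already planned. The arms may end slightly unequal, and the main summary will include some extra training and some early reassessments, which is why it is also shown without the early ones and per protocol. Spare envelopes may have to be prepared, since the documents do not say that more than 20 exist.

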## **7.8 Data collection / follow-up examinations in case of premature termination of studies**

If a patient has to stop, he will be examined by a doctor on the same day. The reassessments of the physiotherapy (BBS and 10m walk test) will take place on the following treatment day if the patient has not been relocated.

## **7.9 accompanying interventions**

There will be no rules for the medications because they are not a contraindication to balance training.

If the patients are in individual balance training, they should not receive a group balance and in the free time also not to train balance.

If the patients are in group balance training, they should not receive any balance training in the individual therapy and in the free time also do not train balance.

During the study period, therefore, the seat-and-stand group will be dropped for both groups, as this is where the balance is trained.

## 8 TEST METHODS

### 8.1 Schedule of study, Table of study measures

one day before arrival	

• Screening of the remittance findings

Day of arrival	

• Admission by the doctors, nursing and physiotherapy --> Screening Inclusion / Exclusion

2nd Day	

• Discussion and presentation of the consent form

• Information to the therapist that the patient may be eligible

• in physiotherapy only BBS and 10 m walk test if patient has already signed

from the 2nd day	

• Signing of consent (SC)

Day of SC	

• Envelopes draw IB or GB for the allocation

• Report to the scheduling about allocation and notification of the patient

SC +1d	

• Assessment Primary target: Gait speed through 10 m walk test

• Assessment secondary target: Fall risk due to BBS, walkability due to FAC

SC +2d	

• IB or GB so that it can be found twice a week (see point 8.2)

6. IB/GB	

• next day reassessments

• 10 m walk test, BBS, FAC

Visitation	

• see point visitation plan

## 8.2 Recording of the target values

The first introduction and training of the assessments took place in January 2018. Therefore, all physiotherapists have at least half a year of practical experience with the tests. A second training took place in February 2018 to discuss questions and to review the standardized procedure. A third review took place in November 2018.

### Walking speed

The walking speed is measured using the 10m walk test. This has a high reliability for stroke patients (Flansbjerg, Holback, Downham, Patten, & Lexell, 2005).

The patient walks a distance of 20m. The start and end points are each marked with a cone. The patient is asked to walk this route as fast as possible, but so that he feels safe. The measurement begins as soon as one of the lower extremities crosses the 5m mark and stops when one of the lower extremities crosses the 15m mark. The therapist goes with the patient to see this. This is to exclude the startup and stopping delays (Schädler, et al., 2012). Three consecutive passes are taken to calculate the mean.

This gives you the walking speed in m / sec if you calculate 10m divided by the seconds. If an aid was needed to go, this will be noted.

This test has high reliability with an ICC of 0.94-0.97 (Flansbjerg, Holback, Downham, Patten, & Lexell, 2005).

In addition, stroke abilities were classified as having everyday abilities (Perry, Garrett, Gronley, & Mulroy, 1995).

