# **7 PARTICIPANTS**

Adult patients with strokes from rehabilitation phase B are recruited as long as they are able to walk with aids. It is a monocentric study in the RehaClinic Kilchberg. There, a total of 20 patients will be recruited over a 3-month period. Since it is a pilot study, I would look for a solution in the discussion, if the number of participants would not be reached. The patients who are already inpatients are recruited insofar as the discharge date is far enough in the future and the patients who have recently arrived there.

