## **7.1 Eligibility criteria**

### **7.1.1 Inclusion criteria**

Patients who meet all of the following inclusion criteria may be included in the clinical trial.

- min. 18 years
- stroke starting from Rehaphase B
- ability to understand therapy instructions
- walkable with aids

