### **7.1.2 Ausschlusskriterien**

If one or more of the following exclusion criteria is met, the individual can not be included in the clinical trial.

- Neurodegenerative disease
- non-stroke dizziness
- cardiopulmonary insufficiency
- polyneuropathy
- peripheral vascular disease
- Known or suspected non-compliance with the protocol, drug or alcohol use
- Inability of the patient to follow the experimental procedure, e.g. because of language problems, mental illness, dementia etc.

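### Entry requires only walking with an aid, yet the primary endpoint needs three 20 m walks, and the section 8.1 order lets a patient be randomised before it is known that the test can be done

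*Combined protocol and SAP*

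**What the plan says.** **Entry.** Section 7.1.1 asks that the patient be "walkable with aids". Section 7 repeats this: "Adult patients with strokes from rehabilitation phase B are recruited as long as they are able to walk with aids". Neither gives a distance or a number of repetitions, and neither requires a walk test. The nearest exclusion, in section 7.1.2, is "Inability of the patient to follow the experimental procedure, e.g. because of language problems, mental illness, dementia etc"; its examples do not concern walking capacity.

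**Endpoint.** Under Walking speed in section 8.2, "The patient walks a distance of 20m", with the middle 10 m timed at the fastest speed the patient feels is safe. Then "Three consecutive passes are taken to calculate the mean". No rule covers a patient who completes none, one or two of them.

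**Order of events.** In section 8.1 the row for the day of consent reads "Envelopes draw IB or GB for the allocation", and the row for one day later reads "Assessment Primary target: Gait speed through 10 m walk test". Other parts of the protocol differ (see the working).

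**Incomplete data.** Section 10.4: "If the data can not be completed, the patient is excluded so as to avoid falsification of the results".

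**The concern.** A patient can satisfy every entry criterion by walking a short distance with a frame or stick and still be unable to produce the primary endpoint. If the envelope has already been opened, that patient has been randomised and is then at risk of removal for a reason that existed, and could have been detected, before allocation.

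Two things are at stake. First, a trial of 10 per arm loses randomised patients for a reason unrelated to training, and the losses fall on the weakest walkers. Second, this pilot is meant to test feasibility and to supply the inputs for sizing a larger trial (synopsis, sections 4.1 and 10). The spread of walking speed would come from a group selected after randomisation, and the same entry rule could be carried into the larger trial.

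The point concerns entry and the baseline test only. Loss of walking ability during the trial is a separate matter.

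**Working it through.** **1. What the endpoint demands.** Three passes of 20 m: 3 x 20 = 60 m in all. Required at entry: walking with aids, no distance stated. The criterion therefore does not secure the capacity that the endpoint needs.

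**2. When the baseline test happens relative to the envelope.**

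| Place | Order |
|---|---|
| Section 8.1, day-of-consent row and the row one day later | Envelope first, walk test the next day |
| Section 8.1, second-day row | Walk test possible on that day if consent is already signed |
| Section 6.1 | Randomisation follows consent; the initial assessment is planned accordingly |
| Section 7.3 | Signed consent is taken to a supervisor, who opens the envelope; no test mentioned |
| Synopsis, Timeplan | Test on the day of signing or the day after, named before the envelope |
| Visitation plan | Assessments and randomisation both in visit 1, order not given |

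These do not agree. Sections 6.1, 7.3 and the main rows of 8.1 tie randomisation to consent; the synopsis can be read as putting the test first.

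**3. What follows under each order.** Envelope first: a patient who cannot do the test is found after allocation, and section 10.4 may then exclude that patient. Test first: the inability is seen in time, but completing the test is not an eligibility criterion, so nothing in the text prevents the envelope from being opened. The gap exists on both readings.

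**4. Size.** Section 10.2 gives 10 + 10 = 20, set by the time available. It states no alpha, power, SD or dropout rate, so only this sum can be reproduced. The share p of eligible patients unable to do the test is not in the documents; I assume 5% to 20%.

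Expected number affected = 20p. Chance that at least one is affected = 1 - (1 - p)^20.

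| Assumed p | Expected affected | Left of 20 | Chance of at least one |
|---|---|---|---|
| 5% | 1 | 19 | 64% |
| 10% | 2 | 18 | 88% |
| 20% | 4 | 16 | 99% |

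Precision if those patients are not replaced and the losses are equal in the two arms. The half-width of a 95% interval for the arm difference, in SD units, is t(0.975, n1+n2-2) x sqrt(1/n1 + 1/n2):

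- 10 v 10: 2.101 x 0.447 = 0.940
- 9 v 9: 2.120 x 0.471 = 0.999, ratio 1.064
- 8 v 8: 2.145 x 0.500 = 1.072, ratio 1.141

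The upper 95% limit for the SD that would feed the sample-size calculation is sqrt(df / chi-square(0.025, df)) times the estimate: 1.48 at 18 df, 1.52 at 16 df and 1.58 at 14 df.

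**The case against.** The other side has several fair points.

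- **The order is contradictory, not fixed.** A reader of the main rows of section 8.1 might infer that the walk is always first attempted the day after randomisation. The synopsis and the second-day row of the same table do not support that. This stands, and the point is limited accordingly.
- **A partial test is not expressly void.** A reader might infer that one or two completed passes give no baseline value and are discarded. Section 8.2 does not say so; that is a reading of it together with section 10.4. What remains is that no scoring rule exists, so the decision would be made case by case in an open trial whose analysis is done by the investigator.
- **Some safeguards exist at entry.** Physiotherapy takes part in the admission screening (8.1), section 8.3.1 allows testing where necessary to check criteria, and the exclusion list in 7.1.2 is open-ended. These make a patient who can walk only a few metres less likely to enter. None states a distance.
- **Replacement.** Section 7.4 replaces participants who stop early, if possible. If it were applied here, 10 per arm would be restored and the loss of precision would disappear. But a failed baseline test is not among the listed reasons, and replacement does not undo an exclusion made after randomisation.
- **No systematic tilt between arms.** A reader might infer that the comparison is biased towards one arm. Inability at baseline precedes training, so in expectation it falls equally on both. The effect is a narrower population plus chance imbalance.
- **This is a pilot.** Failed tests would themselves be a feasibility finding, and section 10 plans no confidence interval. Both are true; the interval serves here only as a measure of lost information.

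**Conclusion.** The point holds in a limited form and is worth correcting. The entry criterion does not secure the capacity that the primary endpoint requires. The documents disagree on whether the baseline test precedes the envelope, and no text makes a failed test a bar to randomisation or says how an incomplete one is scored. Under the section 8.1 order, a randomised patient can be removed for a limitation that was detectable before allocation.

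The size depends on an assumed rate. At 5% to 20%, 1 to 4 of 20 patients are affected. With no replacement, losing 1 or 2 per arm widens the 95% interval by about 6% or 14%. If all are replaced, the numbers recover and only the post-randomisation exclusion remains.

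A reader might also infer, from the reliability of 0.94-0.97 quoted in section 8.2, that averaging three passes adds little. The documents do not say whether that figure refers to a single pass or to a session, so they do not support the inference. Three passes can stay as the target.

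**What to change.** 1. Reconcile the synopsis and sections 6.1, 7.3 and 8.1 so that the baseline 10 m walk test is completed after consent and before the envelope is opened. Add to section 7.1.1 that the patient completes at least one 20 m pass of that test, with or without an aid.
2. In section 8.2, keep three passes as the target. State that a patient with one or two completed passes stays in the analysis, that the number of passes is recorded, and that the change score uses the same number of first passes at both visits. Without that matching, one pass at baseline could be set against the mean of three at reassessment, and practice or fatigue across passes could distort the change.

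The cost is a few sentences and no new assessment, since the baseline test is already planned. A few very limited walkers will be screened out, recruitment may be slightly slower, and speeds based on fewer passes are slightly less precise. Patients who fail the test before the envelope can be counted in the screening log (section 12.1.1), so the feasibility information is kept.
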